9.4 Detection of Bias

This study has been designed to minimize potential bias by the use of randomization of subjects into treatment groups and the use of blinding. Other factors that may bias the results of the study include:

- major protocol deviations likely to impact the analysis and interpretation of the efficacy endpoints
- subject level unblinding before final database lock and formal unblinding
- DMC related analyses

Important protocol deviations likely to impact the analysis and interpretation of the efficacy endpoints will be tabulated in the Clinical Study Report (CSR).

Any unblinding of individual subjects prior to formal unblinding of the study will be documented in the CSR. The impact of such unblinding on the results observed will be assessed. Data from subjects whose treatment assignments are unblinded prior to formal unblinding will be listed. The timing and reason for unblinding will be included in these listings.

Additional sensitivity analyses may be included to assess the impact of potential biases on the primary endpoint. If any sensitivity analyses are required to evaluate potential biases in the study's conclusions, then the sources of the potential biases and results of the sensitivity analyses will be documented in the CSR.

9.5 Outliers

Various methods, including univariate summaries, histograms, scatter plots, box plots, and line graphs, may be used to identify outliers in key safety and efficacy variables. Extreme data points will be identified during the blinded review of the data prior to database lock. Such data points will be reviewed with clinical data management to

Statistical Analysis Plan: 20130286

Date: 20 January 2019 **Page 20 of 35**

ensure accuracy. The primary analyses will include outliers in the data. Sensitivity analyses may be undertaken if extreme outliers for a variable are observed.

9.6 Distributional Characteristics

Distributional assumptions for the primary and secondary co-endpoints will be assessed. If the assumptions are not met, then alternative methods will be utilized. The use of alternative methods will be fully justified in the CSR.

9.7 Validation of Statistical Analyses

Programs will be developed and maintained, and output will be verified in accordance with current risk-based quality control procedures.

Tables, figures, and listings will be produced with validated standard macro programs where standard macros can produce the specified outputs.

The production environment for statistical analyses consists of Amgen-supported versions of statistical analysis software; for example, the SAS System version 9.2 or later.

10. Statistical Methods of Analysis

10.1 General Principles

To evaluate efficacy and safety of 24 weeks of evolocumab 420 mg QM compared with placebo, the primary analysis will be performed when all randomized subjects in the double-blind treatment period have either completed all the scheduled study visits in the double-blind treatment period or have early terminated from the study. Data will be locked at each clean snapshot (the primary analysis and final analysis).

Based on the locked snapshot for the primary analysis, efficacy and safety analyses will be performed on FAS unless otherwise specified, and data will be summarized by randomized treatment group. Data occurring after the first dose of open-label evolocumab will be excluded from the primary analysis dataset.

The final analysis will be performed when all subjects have completed all scheduled study visits in the open-label period or have early terminated from the study. Based on the final locked snapshot for the final analysis, long-term efficacy and safety analyses will be performed on LAS and the analyses will be descriptive. Safety endpoints and exploratory endpoints will be evaluated for the open-label period and summarized overall and by treatment in the double-blind period.

Statistical Analysis Plan: 20130286

Page 21 of 35 Date: 20 January 2019

Subject disposition, demographics, baseline characteristics, and exposure to IP will be summarized by treatment group. Summary statistics for continuous variables will include the number of subjects, mean, median, standard deviation or standard error, minimum, and maximum. For categorical variables, the frequency and percentage will be given.

Methods of handling missing data for efficacy endpoints are described below. Missing data will not be imputed for safety endpoints.

Multiplicity Adjustment Method

Methods of adjusting for multiplicity due to multiple endpoints (primary and secondary efficacy endpoints) in order to preserve the familywise error rate at 0.05 are described in Figure 1.

[figure not shown]

Figure 1. Multiplicity Adjustment Methods

Statistical Analysis Plan: 20130286

Date: 20 January 2019 Page 22 of 35

The following method will be used to preserve the family-wise error rate for the primary and secondary endpoints:

1. If the treatment effect from the primary analysis of the primary endpoint is significant at a significance level of 0.05, statistical testing of the tier 1 secondary efficacy endpoints will follow the Hochberg procedure at a significance level of 0.005 (Hochberg, 1988)

- 2. If all tier 1 secondary efficacy endpoints are significant, the tier 2 secondary efficacy endpoints will be tested using the Hochberg procedure at a significance level of 0.05.
- 3. If not all tier 1 secondary efficacy endpoints are significant, the tier 2 secondary efficacy endpoints will be tested using the Hochberg procedure at a significance level of 0.045 (Wiens, 2003).

Unless specified otherwise, all other hypothesis testing will be 2-sided with a significance level of 0.05.

10.2 Subject Accountability

The number and percent of subjects who were screened, randomized, received IP, completed IP, discontinued IP and reasons for discontinuing, completed treatment period, discontinued study and reasons for discontinuing will be summarized by treatment group.

Key study dates for the first subject enrolled, last subject enrolled and last subject's end of double-blind IP, last subject's end of open-label IP and last subject's end of study will be presented.

The number and percent of subjects randomized will be tabulated by the stratification factors.

The number of subjects included in and excluded from each analysis set and reason for exclusion will also be summarized.

10.3 Important Protocol Deviations

Important Protocol Deviations (IPDs) categories are defined by the study team before the first subject's visit and updated during the IPD reviews throughout the study prior to database lock. These definitions of IPD categories, sub-category codes, and descriptions will be used during the course of the study. Eligibility deviations are defined in the protocol.

Statistical Analysis Plan: 20130286

Date: 20 January 2019 **Page 23 of 35**

10.4 Demographic and Baseline Characteristics

Demographic (ie, age, age group [< 65, >= 65], sex, race, ethnicity) and baseline disease characteristics (cardiovascular medical history, HIV medical history, laboratory parameters, antiretroviral therapy and lipid-regulating medication) will be summarized by treatment group and overall using descriptive statistics. If multiple races have been reported for a subject, the subject will be categorized as multiple race.

Statistical Analysis Plan: 20130286

Date: 20 January 2019 **Page 24 of 35**

10.5 Efficacy Analyses

The following table summarizes the key efficacy analyses that will be conducted for the primary analysis

Table 2. Key Efficacy Analyses Summary Table

Endpoint Primary Endpoint	Primary Summary and Analysis Method (Specify Analysis Set if FAS is Not Used)	P-values from the Statistical Tests	Hierarchical Testing Procedure for testing of Treatment Effect vs. Placebo. as specified in the Multiplicity Adjustment Method diagram	Sensitivity Analysis
Percent change from baseline at week 24 in LDL-C	Repeated measures model	P1	P1 compare to α = 0.05	 Non-parametric analyses will be performed Multiple imputation for subjects who discontinue evolocumab and are missing primary endpoint data.
Secondary Endpoints (Tier				
 LDL-C achievement at week 24 LDL-C response at week 24 	Cochran Mantel-Haenszel (CMH) test	P2a	If P1 < 0.05, → P2a for each tier 1 endpoint will be tested through Hochberg method with α = 0.005	
 Change from baseline at week 24 in LDL-C Percent change from baseline at week 24 in: non-HDL-C ApoB total cholesterol 	Repeated measures model	P2a	Else (ie, primary endpoint is not significant) → No further testing	

Page 1 of 2

Footnotes are defined on next page of the table

Statistical Analysis Plan: 20130286

Date: 20 January 2019 **Page 25 of 35**

Table 2. Key Efficacy Analyses Summary Table

Endpoint Secondary Endpoints (T	Primary Summary and Analysis Method (Specify Analysis Set if FAS is Not Used)	P-values from the Statistical Tests	Hierarchical Testing Procedure for testing of Treatment Effect vs. Placebo. as specified in the Multiplicity Adjustment Method diagram	Sensitivity Analysis
Percent change from baseline at week 24 in: Lp(a) Triglycerides HDL-C VLDL-C	Repeated measures model	P2b	If all P2a values are significant through Hochberg method, → all P2b values will be tested through Hochberg method with α = 0.05 Else (ie, not all tier 1 endpoints are significant), → all P2b values will be tested through Hochberg method with α = 0.045	

Page 2 of 2

Supportive analysis: the primary analysis will be repeated using the CAS.

Statistical Analysis Plan: 20130286

Date: 20 January 2019 Page 26 of 35

10.5.1 Analyses of Primary Efficacy Endpoint

10.5.1.1 Primary Analysis of Primary Endpoint

To assess the primary endpoint of the percent change from baseline in LDL-C at week 24, a repeated measures linear effects model will be used on the FAS to compare the efficacy of evolocumab with placebo. The repeated measures model will include terms for treatment group, stratification factors, scheduled visit and the interaction of treatment with scheduled visit. All LDL-C values observed will be used irrespective of whether a subject remained on IP, and missing values will not be imputed for primary analysis. If there are fewer than 5 subjects in one stratum, then the Hepatitis C status stratification factor will not be included in the repeated measures model. To account for the repeated LDL-C measurements within a subject across the visits, the repeated measures linear effects model will use an unstructured covariance.

Multiplicity adjustment procedures are defined in Section 10.1.

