The statistical model and testing of the tier 1 secondary efficacy endpoints will be similar to the primary analysis of primary endpoints. The secondary endpoint of LDL-C response (50% reduction of LDL-C from baseline and achievement of target LDL-C < 70 mg/d Las defined in secondary endpoint section) will be analyzed using the Cochran-Mantel Haenszel test adjusted by the stratification factors.

Analysis of the tier 2 secondary efficacy endpoints will use the same analysis model as the tier 1 endpoints.

Multiplicity adjustment procedures are defined in Section 10.5.1.1.

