3.2 Sample Size

The planned sample size for the comparison between evolocumab 420 mg QM and placebo at a ratio of 2:1 in the double-blind treatment period is 450 total subjects.

The primary analysis will require the 2-sided tests of the primary endpoint to be significant at a level of 0.05. The planned sample size should provide adequate power to determine the superiority of evolocumab 420 mg QM relative to placebo as measured by the primary endpoint. From the integrated efficacy analysis of completed phase 3 studies, the treatment effect of evolocumab 420 mg QM compared to placebo and the corresponding 95% confidence interval at the mean of weeks 10 and 12 was -64.98% [-69.51%, -60.45%], with treatment effect ranges between -55.1% and -62.33% from Studies 20110114, 20110115, and 20110117. The assumed treatment effect between the primary endpoint in evolocumab 420 mg QM is 40%, with a common standard deviation (SD) of 20%. This SD assumption is based on evolocumab phase 3 results.

This sample size will provide approximately 99% power for the primary endpoint in testing the superiority of evolocumab dose regimen over placebo, assuming a dropout rate of 10%.

In addition, 300 subjects in the evolocumab 420 mg QM group will provide approximately 95% probability of detecting adverse events that occur at a rate of 1%.

It is expected that the proportion of subjects assigned to the no statin use at baseline stratum will be approximately 10%. In this stratum, 30 subjects in the evolocumab 420 mg QM group will provide approximately 79% probability of detecting adverse events that occur at a rate of 5%.

4. Study Endpoints and Covariates

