4.2 Planned Covariates

Baseline covariates include:

- Stratification factors in Double-blind Treatment Period:
 - Statin use at baseline (yes/no)
 - Hepatitis C status (yes/no)
- Age
- Sex
- Race (black, white, and other)
- LDL-C
- Family history of premature coronary heart disease (yes/no)
- •
- Region (North America, Europe, other)
- Body Mass Index (BMI)
- Glucose tolerance status (type 2 diabetes mellitus, metabolic syndrome, neither type 2 diabetes mellitus nor metabolic syndrome)
- Hypertension (yes, no)
- Current smoker (yes, no)
- Baseline CHD risk factors ≥ 2 (yes, no)
- Triglycerides
- NCEP high risk (yes, no)
- Statin intensity (High/Moderate/Low intensity as per ACC/AHA guidelines)
- Lipid entry target (above both non-HDL-C and LDL-C entry criteria thresholds, above non-HDL-C entry criteria threshold only, and above LDL-C criteria threshold only)
- Protease inhibitor use

5. Hypotheses and/or Estimations

The null hypothesis is that there is no mean difference in the mean percent change from baseline at week 24 in LDL-C between evolocumab 420 mg QM and placebo, and the alternative hypothesis is that a mean difference does exist.

6. Definitions

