6.2 Demographics and Baseline Related Definitions

Age

Subject age at enrollment will be collected in years in the clinical database.

Statistical Analysis Plan: 20130286

Date: 20 January 2019 **Page 13 of 35**

Baseline Lipid and Lipid-related Parameters

Baseline values for fasting lipids (total cholesterol, HDL-C, LDL-C, VLDL-C and triglycerides), ApoA1, ApoB, Lp(a) and their derived parameters (eg, ratio between them) are defined as the mean of the two most recent non-missing fasting concentrations measured through central lab prior to or on Study Day 1. If for any reason only 1 value is available, then that value will be used as baseline.

Other Baseline Values

The baseline value is defined as the last non-missing value collected prior to or on Study Day 1.

Change (absolute change) from Baseline

The arithmetic difference between a post-baseline value and baseline for a given time point:

Change (absolute change) from baseline = (post-baseline value – baseline value)

Percent Change from Baseline

The percent change from baseline for a given variable at a given time point is defined as:

100 x [(value at given time point – baseline value) / baseline value]

Baseline Metabolic Syndrome

For each subject without type 2 diabetes mellitus, metabolic syndrome is identified by the presence of 3 or more of the components listed below (modified AHA/NHLBI criteria). Subjects with type 2 diabetes cannot be categorized as having metabolic syndrome.

Risk Factor	Defining Level
Elevated waist circumference:	
Non-Asian:	
Men	≥ 102 cm
Women	≥ 88 cm
Asian:	
Men	≥ 90 cm
Women	≥ 80 cm
Triglycerides	≥ 150 mg/dL
HDL cholesterol	
Men	< 40 mg/dL
Women	< 50 mg/dL
Blood Pressure	SBP ≥ 130 mmHg or DBP ≥ 85 mmHg
	OR Hypertension checked 'yes' on
	Cardiovascular Medical History eCRF
Fasting glucose	≥ 100 mg/dL

Statistical Analysis Plan: 20130286

Date: 20 January 2019 Page 14 of 35

Baseline CHD Risk Factors

A subject will be categorized as having 2 or more CHD Risk Factors (Y/N) from the list of the modified NCEP ATP III risk factors:

- current cigarette smoking
- hypertension
- type II diabetes mellitus
- family history of premature CHD as recorded on the Cardiac Risk Factors eCRF
- low HDL-C defined as baseline HDL-C < 40 mg/dL in men and < 50 mg/dL in women.

Baseline National Cholesterol Education Program (NCEP) Risk Categories

Risk Factor	Defining Level	

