10.5.1.3 Covariate and Subgroup Analyses of Primary Endpoints

As a supportive analysis, the primary analysis will be repeated using the CAS to estimate the on-treatment treatment effect.

In addition to the primary analysis specified in Section 10.5.1.1, covariate-adjusted analyses of the primary efficacy endpoint will be performed as supportive analyses using the baseline covariates in Section 4.2 in their original format, one at a time, in the primary model used in the primary analyses as appropriate.

Statistical Analysis Plan: 20130286

Date: 20 January 2019 **Page 27 of 35**

Subgroup analyses on the primary efficacy endpoint will be conducted using the subgroups specified in Section 7.3. Depending on the distribution of baseline LDL-C, analyses using different subgroups of baseline LDL-C will be performed if applicable. Treatment effect differences among subgroups, which represent subgroup by treatment interactions, will be estimated and tested based on statistics from the subgroup repeated measures models.

For covariate and subgroup analyses, the stratification factors from the eCRF will be used. Differences in stratum assignment between data collection via IVRS and eCRF will be tabulated.

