10.5.2 Analyses of Secondary Efficacy Endpoints

The statistical model and testing of the secondary efficacy endpoints (change from baseline and percent change from baseline) will be similar to the primary analysis of the primary endpoint. The secondary endpoints of achievement of target LDL-C < 70 mg/dL at week 24 and LDL-C response of 50% reduction of week 24 LDL-C from baseline will be analyzed using the Cochran-Mantel Haenszel test adjusted by the stratification factors.

Multiplicity adjustment procedures are defined in Section 10.1.

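### The confirmatory repeated-measures models omit the baseline value of the lipid analysed; adding it is a cheap gain in precision, mainly for absolute LDL-C change

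*SAP*

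**What the plan says.** SAP 10.5.1.1 and protocol 10.5.2 list the same model terms: "The repeated measures model will include terms for treatment group, stratification factors, scheduled visit and the interaction of treatment with scheduled visit". The stratification factors are entry statin use and hepatitis C status, neither of which is a lipid level. SAP 10.5.1.1 adds an unstructured covariance across visits.

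Baseline LDL-C is on the covariate list in SAP 4.2, but SAP 10.5.1.3 gives that list a limited role: "covariate-adjusted analyses of the primary efficacy endpoint will be performed as supportive analyses using the baseline covariates in Section 4.2", one covariate at a time.

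The eight continuous secondary endpoints are absolute LDL-C change and percent change in non-HDL-C, ApoB and total cholesterol (tier 1), and percent change in Lp(a), triglycerides, HDL-C and VLDL-C (tier 2). Protocol 10.5.3 says of tier 1: "The statistical model and testing of the tier 1 secondary efficacy endpoints will be similar to the primary analysis of primary endpoints". Tier 2 follows tier 1. SAP 10.5.2 says much the same ("change from baseline and percent change from baseline) will be similar to the primary analysis of the primary endpoint"), and SAP Table 2 says only "Repeated measures model". None of these names a baseline term.

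SAP 6.2 defines baseline lipids as "the mean of the two most recent non-missing fasting concentrations measured through central lab prior to or on Study Day 1", or a single value if only one is available.

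**The concern.** Baseline is measured with error, being the mean of at most two fasting values, and it is subtracted (and, for percent change, divided by) to form the response. Noise in baseline therefore enters the response, so baseline predicts change. Using a change score does not remove that dependence. Nor does the unstructured covariance, because baseline is not one of the modelled responses.

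Leaving the term out gives wider intervals than the collected data allow, and an estimate that moves with any chance baseline difference between arms. Absolute LDL-C change is the most exposed: it depends strongly on baseline, it is a tier 1 endpoint, and no adjusted analysis of it is stated. An adjustment chosen after unblinding would carry less weight than a prespecified one.

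**Working it through.** **1. The plan's own figure.** SAP 3.2 assumes a 40-point effect "with a common standard deviation (SD) of 20%. This SD assumption is based on evolocumab phase 3 results", with 450 subjects randomized 2:1 and 10% dropout. Evaluable: 450 × 0.9 = 405, or 270 and 135.

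- Standard error: 20 × √(1/270 + 1/135) = 2.11 points; 95% half-width 1.96 × 2.108 = 4.13.
- Effect in standard errors: 40 / 2.11 ≈ 19.
- Computed power exceeds 99.9%, consistent with the stated figure of about 99%. The design has 99% power for (1.960 + 2.326) × 2.108 = 9.0 points.

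The question is therefore precision, not power.

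**2. Why baseline explains variance: an approximate calculation.** The documents give no between- or within-subject CV and no mean baseline LDL-C. I assume a between-subject CV b of 25 to 40% and a within-subject CV w of 18.5%, and work in units of mean baseline. Baseline is the mean of two values. Evolocumab leaves 0.6 of the true level.

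With b = 0.25: w² = 0.0342, w²/2 = 0.0171, and baseline variance S = 0.0625 + 0.0171 = 0.0796. For absolute change:

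- Placebo slope on baseline: −0.0171 / 0.0796 = −0.215. Variance: 1.5 × 0.0342 = 0.0513.
- Evolocumab slope: 0.6 × 0.0625 / 0.0796 − 1 = −0.529. Variance: 0.16 × 0.0625 + 0.36 × 0.0342 + 0.0171 = 0.0394.
- Common fitted slope at 2:1: β = (2 × −0.529 − 0.215) / 3 = −0.424.
- Residual variance in arm j: V_j − S(2ββ_j − β²), giving 0.0511 (placebo) and 0.0180 (evolocumab).
- Variance ratio, adjusted to unadjusted, weighting placebo twice: (0.0180 + 2 × 0.0511) / (0.0394 + 2 × 0.0513) = 0.85.

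For percent change, to first order, the slopes are −0.215 and 0.6 × −0.215 = −0.129, and the same steps give 0.93. With b = 0.40 the ratios are 0.89 (absolute) and 0.97 (percent). The implied unadjusted standard error for percent change, √(0.36 × 0.0513/270 + 0.0513/135), is 2.12 points, which matches the plan.

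**3. Simulation of the planned model.** Set-up: 300 vs 150 subjects; weeks 12 and 24; unstructured covariance; statin (10% not on statin) and hepatitis C (10% assumed) terms; 10% missing at week 24 completely at random; lognormal values; 2,500 replicates in each of 16 scenarios. These crossed b of 25 or 40%, a no-statin to statin baseline ratio of 1.0 or 1.4, and the four rows below. Scenario A has no between-subject variation in response and w of 18 to 19%; it matches the plan's standard error, with SDs of about 22.5 (placebo) and 13.5 (evolocumab). Scenario B has SD 20 in both arms, w of 16 to 17% and a response CV of about 26%. The entry cut-off drops the lowest 30% of screening values, an assumed stand-in for inclusion criterion 107.

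| Scenario | Variance ratio, percent change | Variance ratio, absolute change |
|---|---|---|
| A | 0.945–0.978 | 0.850–0.884 |
| A, entry cut-off | 0.965–0.988 | 0.871–0.898 |
| B | 0.967–0.989 | 0.890–0.915 |
| B, entry cut-off | 0.980–0.995 | 0.908–0.924 |

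**4. Interval width.** The half-width scales with the square root of the ratio.

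- Percent change: 1 − √0.995 = 0.25% to 1 − √0.945 = 2.8%, or 0.01 to 0.11 points on about 4.1.
- Absolute change: 1 − √0.924 = 3.9% to 1 − √0.850 = 7.8%. In evaluable subjects this equals 405/0.924 − 405 = 33 to 405/0.850 − 405 = 71 more.

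**5. Chance imbalance.** The 95% limit is 1.96 × √(1/300 + 1/150) = 0.196 baseline SD. In step 2 with b = 0.25 this moves the unadjusted absolute change by 0.424 × √0.0796 × 0.196 = 2.3% of mean baseline. Across the simulated scenarios the shift is 1.8 to 3.0% for absolute change and 0.34 to 0.89 points for percent change.

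**6. Standard errors.** Coverage of nominal 95% intervals:

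| Standard error and scenario | Unadjusted | Adjusted |
|---|---|---|
| Model-based, A, percent change | 0.902–0.916 | 0.897–0.918 |
| Model-based, A, absolute change | 0.932–0.950 | 0.899–0.922 |
| Model-based, B, both endpoints | 0.940–0.968 | 0.938–0.953 |

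With sandwich standard errors, coverage was 0.941 to 0.961 in every model and scenario.

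**The case against.** The strongest reply is that nothing the trial will conclude depends on this. The planned model is valid, absolute LDL-C change sits at about 16 to 18 standard errors in the simulations, and SAP 10.5.1.3 already yields a baseline-adjusted primary estimate. All of that stands, and it makes this a recommendation rather than a correction.

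The size also depends on assumed CVs. The scenario closest to the plan (common SD of 20, with an entry cut-off) gives the smallest variance cuts: 0.5 to 2.0% for percent change and 7.6 to 9.2% for absolute change. That stands too. The upper figures need unequal arm SDs.

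Only LDL-C was simulated, and seven of the eight secondary endpoints are percent changes, where the LDL-C gain is small. No particular gain is claimed for those seven, tier 2 included; the case for treating them alike is consistency at negligible cost.

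The baseline term alone can do harm: with unequal arm variances and model-based standard errors it lowers coverage for absolute change. This is correct and is why the fix pairs it with sandwich standard errors. Under a common SD they are not strictly needed, but equal variances cannot be counted on. The simulation assumed data missing completely at random, whereas SAP 9.3.2 relies on missing at random.

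Finally, the imbalance shift is part of the same sampling variance as the interval width, so the two gains must not be added together.

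**Conclusion.** The point holds. The confirmatory models contain no baseline lipid term, adjustment for baseline LDL-C is supportive and confined to the primary endpoint, and none is stated for the eight continuous secondary endpoints. This is forgone precision, not an error. For LDL-C, the 95% interval would narrow by 3.9 to 7.8% for absolute change and by 0.2 to 2.8% for percent change. These sizes rest on assumed between-subject CVs of 25 to 40%, within-subject CVs of 16 to 19%, and calibration to the plan's SD of 20. The direction does not depend on the exact values; the size does.

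**What to change.** Before unblinding:

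- Add the baseline value of the analysed lipid, and its interaction with visit, to every repeated-measures model in SAP 10.5.1.1 and 10.5.2.
- Specify empirical (sandwich) standard errors for all of these models. The baseline term should not be added without them.
- Keep the present model without baseline as a sensitivity analysis, also with sandwich standard errors.
- Record the departure from protocol 10.5.2 in SAP Section 11.

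The cost is two or three lines in the SAP and program and one extra parameter per visit. No new data are needed, since the baseline values are already collected.
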